### **Secondary Endpoint #3**

Endpoint Description: Time to first non-elective all-cause hospitalization

Response Variable Definition: Time to first non-elective hospitalization will be defined as the time to first non-elective hospitalization. The hospitalizations will be reviewed and adjudicated by a CEC as non-elective all-cause hospitalizations. All patients will have some information regarding mortality and last visit of follow-up. Patients without any observed event at the time of analysis will be censored at their last visit, death, or lung transplantation.

Additional Covariates: Age, sex, baseline DLCO, baseline FVC, use of NAC at enrollment, use of standard of care medications at enrollment, and choice of antimicrobial agent prior to randomization.

Handling of Dropouts and Missing Data: The censoring mechanism is assumed to be non-informative. Supportive analyses will be performed to assess the impact of a potential informative censoring.

Diagnostic tests: The additional continuous covariates to be used in the primary analysis model will be assessed for major departures from linearity by inspection of restricted cubic spline plots. If a departure is observed then a suitable transformation will be explored. In addition the proportional hazard assumptions will be explored by inspection of Martingale residuals plots. If a major departure is observed then the variable will added to the model as a stratification variable.

Statistical Tests: The Cox proportional hazards regression model will be used to estimate outcome differences between the two treatment arms: “Standard care + oral antimicrobial therapy” and “Standard care”. The outcome is the time to first non-elective all-cause hospitalization with model terms for treatment arm, baseline measurement, and covariates. Hazard ratios and 95% confidence intervals will summarize the differences between treatment arms.

Interpretation of Results: For Cox regression models a hazard ratio below 1.00 will indicate a reduction in events for “Standard care + oral antimicrobial therapy” arm. A hazard ratio above 1.00 will indicate increase in events for “Standard care + oral antimicrobial therapy” arm.

### **Secondary Endpoint #4**

Endpoint Description: Total number of non-elective respiratory hospitalizations

Response Variable Definition: The hospitalizations will be reviewed and adjudicated by a clinical events committee (CEC) as non-elective respiratory hospitalizations.

Additional Covariates: Age, sex, baseline DLCO, baseline FVC, use of NAC at enrollment, and choice of antimicrobial agent prior to randomization.

Handling of Dropouts and Missing Data: All patients will have some information regarding mortality and last visit of follow-up. Lung transplantation will be additional censoring variable in this analyses. The censoring mechanism is assumed to be non-informative. Supportive analyses will be performed to assess the impact of a potential informative censoring.

Diagnostic tests: The additional continuous covariates to be used in the primary analysis model will be assessed for major departures from linearity by inspection scatter plots with LOESS curves. If a departure is observed then a suitable transformation will be explored. The validity of this model in terms of meeting modeling assumptions will be assessed via standard modeling diagnostics and goodness-of-fit measures.

Statistical Tests: A Poisson regression model will be used to estimate outcome ratio between the two treatment arms: “Standard care + oral antimicrobial therapy” and “Standard care”. The outcome is the total number of non-elective respiratory hospitalizations with model terms for treatment arm, baseline measurement, and covariates. Rates and 95% confidence intervals will summarize the differences between treatment arms.

Interpretation of Results: For poisson regression models a ratio below 1.00 will indicate a reduction in events for “Standard care + oral antimicrobial therapy” arm. A hazard ratio above 1.00 will indicate increase in events for “Standard care + oral antimicrobial therapy” arm.

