11.3 Sample Size Justification

Based on prior work from the study team using IPFnet data, it is anticipated that the event rate in the placebo arm will be highly dependent on the proportion of patients enrolled at the different GAP scores. Given the availability of two FDA-approved drugs for IPF, it is our belief that the study population will be heavily weighted toward GAP scores of 3. In **Table 1**, the statistical power is determined for designs enrolling 500 patients with placebo group events rates varying from 24% to 36% and (12-month) treatment effects varying from 30% to 35%. In

general, the proposed design provides adequate power expect when the 12-month standard-of-care group event rate is 24% and the reduction in events is less than 30%.

Table 1. Statistical Power Assuming a Sample Size of 500 Randomized Patients

Standard-of-care event rate*	Antimicrobial therapy strategy event rate*	One-year Event Rate Reduction	Power
24%	16.8%	30%	78%
30%	21.0%	30%	87%
36%	25.2%	30%	93%
24%	16.0%	33.3%	86%
30%	20.0%	33.3%	93%
36%	24.0%	33.3%	97%
24%	15.6%	35%	89%
30%	19.5%	35%	95%
36%	23.4%	35%	98%

*12-month event rates. Calculations assume a 2-sided Type-I error rate of 0.05. The minimum follow-up is planned to be 12 months and the maximum follow-up is 42 months. Drop-out rates are assumed to be approximately 2% per year. Power calculations were based on a log-rank test with assumed event rates were exponentially distributed. Calculations were computing using nQuery 7.0 software.

We plan to enroll 500 patients over a 30 month window with a minimum of 12 months of follow-up on all patients. **Table 2** shows the required number of endpoint events to have 80% to 90% power with hazard ratios varying from 0.50 to 0.75.

Table 2. Required number of events

	HR=0.50	HR=0.55	HR=0.60	HR=0.65	HR=0.70	HR=0.75
80% power	65	88	120	169	247	379
85% power	75	100	138	194	282	434
90% power	87	118	161	226	330	508

Calculations performed using nQuery 7.0 and assume a 0.05 type I error rate (two-sided) with 1:1 randomization.

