## **Secondary Endpoint #5**

Endpoint Description: Total number of non-elective all-cause hospitalizations

Response Variable Definition: The hospitalizations will be reviewed and adjudicated by a CEC as non-elective all-cause hospitalizations.

Additional Covariates: Age, sex, baseline DLCO, baseline FVC, use of NAC at enrollment, use of standard of care medications at enrollment, and choice of antimicrobial agent prior to randomization.

Handling of Dropouts and Missing Data: All patients will have some information regarding mortality and last visit of follow-up. Lung transplantation will be additional censoring variable in this analyses. The censoring mechanism is assumed to be non-informative. Supportive analyses will be performed to assess the impact of a potential informative censoring.

Diagnostic tests: The additional continuous covariates to be used in the primary analysis model will be assessed for major departures from linearity by inspection scatter plots with LOESS curves. If a departure is observed then a suitable transformation will be explored. The validity of this model in terms of meeting

modeling assumptions will be assessed via standard modeling diagnostics and goodness-of-fit measures.

Statistical Tests: The Poisson regression model will be used to estimate outcome ratio between the two treatment arms: “Standard care + oral antimicrobial therapy” and “Standard care”. The outcome is the total number of non-elective all-cause hospitalizations with model terms for treatment arm, baseline measurement, and covariates. Rates and 95% confidence intervals will summarize the differences between treatment arms.

Interpretation of Results: For Poisson regression models a ratio below 1.00 will indicate a reduction in events for “Standard care + oral antimicrobial therapy” arm. A ratio above 1.00 will indicate increase in events for “Standard care + oral antimicrobial therapy” arm.

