## **Secondary Endpoint #8**

Endpoint Description: Total number of respiratory infections

Response Variable Definition: all lower respiratory tract infection(s) treated with antibiotic treatment will be collected in follow-up.

Additional Covariates: Age, sex, baseline DLCO, baseline FVC, use of NAC at enrollment, use of standard of care medications at enrollment, and choice of antimicrobial agent prior to randomization.

Handling of Dropouts and Missing Data: The censoring mechanism is assumed to be non-informative. Supportive analyses will be performed to assess the impact of a potential informative censoring.

Diagnostic tests: The additional continuous covariates to be used in the primary analysis model will be assessed for major departures from linearity by inspection scatter plots with LOESS curves. If a departure is observed then a suitable transformation will be explored. The validity of this model in terms of meeting modeling assumptions will be assessed via standard modeling diagnostics and goodness-of-fit measures.

Statistical Tests: A Poisson regression model will be used to estimate outcome ratio between the two treatment arms: “Standard care + oral antimicrobial therapy” and “Standard care”. The outcome is the total number of respiratory infections with model terms for treatment arm, baseline measurement, and covariates. Rates and 95% confidence intervals will summarize the differences between treatment arms.

Interpretation of Results: For Poisson regression models a ratio below 1.00 will indicate a reduction in events for “Standard care + oral antimicrobial therapy” arm. A ratio above 1.00 will indicate increase in events for “Standard care + oral antimicrobial therapy” arm.

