Kaplan-Meier Event Rate (95% CI) At 24 Months	xx.x (xx.x, xx.x)	xx.x (xx.x, xx.x)	xx.x (xx.x, xx.x)	x.xxx
# of events/# of Patients	N/N	N/N	N/N	
Kaplan-Meier Event Rate (95% CI)	xx.x (xx.x, xx.x)	xx.x (xx.x, xx.x)	xx.x (xx.x, xx.x)	
Non-elective hospitalization				
Patients with one of more Number per patient	N (xx.x%)	N (xx.x%)	N (xx.x%)	
0	N (xx.x%)	N (xx.x%)	N (xx.x%)	
1	N (xx.x%)	N (xx.x%)	N (xx.x%)	
2	N (xx.x%)	N (xx.x%)	N (xx.x%)	
3	N (xx.x%)	N (xx.x%)	N (xx.x%)	
At 6 Months				x.xxx
# of events/# of Patients	N/N	N/N	N/N	
Kaplan-Meier Event Rate (95% CI)	xx.x (xx.x, xx.x)	xx.x (xx.x, xx.x)	xx.x (xx.x, xx.x)	
At 12 Monthss				x.xxx
# of events/# of Patients	N/N	N/N	N/N	
Kaplan-Meier Event Rate (95% CI)	xx.x (xx.x, xx.x)	xx.x (xx.x, xx.x)	xx.x (xx.x, xx.x)	
At 18 Months				x.xxx
# of events/# of Patients	N/N	N/N	N/N	
Kaplan-Meier Event Rate (95% CI)	xx.x (xx.x, xx.x)	xx.x (xx.x, xx.x)	xx.x (xx.x, xx.x)	
At 24 Months				x.xxx
# of events/# of Patients	N/N	N/N	N/N	
Kaplan-Meier Event Rate (95% CI)	xx.x (xx.x, xx.x)	xx.x (xx.x, xx.x)	xx.x (xx.x, xx.x)	
Respiratory hospitalization				
Patients with one of more Number per patient	N (xx.x%)	N (xx.x%)	N (xx.x%)	
0	N (xx.x%)	N (xx.x%)	N (xx.x%)	
1	N (xx.x%)	N (xx.x%)	N (xx.x%)	
2	N (xx.x%)	N (xx.x%)	N (xx.x%)	
3	N (xx.x%)	N (xx.x%)	N (xx.x%)	

**CLEANUP-IPF Study  
Final Analysis Table 3.1  
Primary Efficacy  
Summary of Events**

Event	Oral antimicrobial therapy N= N NEVAL	Standard Care N= N NEVAL	All Patients N= N NEVAL	P-Value
At 6 Months				x.xxx
# of events/# of Patients	N/N	N/N	N/N	
Kaplan-Meier Event Rate (95% CI)	xx.x (xx.x, xx.x)	xx.x (xx.x, xx.x)	xx.x (xx.x, xx.x)	
At 12 Monthss				x.xxx
# of events/# of Patients	N/N	N/N	N/N	
Kaplan-Meier Event Rate (95% CI)	xx.x (xx.x, xx.x)	xx.x (xx.x, xx.x)	xx.x (xx.x, xx.x)	
At 18 Months				x.xxx
# of events/# of Patients	N/N	N/N	N/N	
Kaplan-Meier Event Rate (95% CI)	xx.x (xx.x, xx.x)	xx.x (xx.x, xx.x)	xx.x (xx.x, xx.x)	
At 24 Months				x.xxx
# of events/# of Patients	N/N	N/N	N/N	
Kaplan-Meier Event Rate (95% CI)	xx.x (xx.x, xx.x)	xx.x (xx.x, xx.x)	xx.x (xx.x, xx.x)	
Respiratory infections				
Patients with one of more	N (xx.x%)	N (xx.x%)	N (xx.x%)	
Number per patient				
0	N (xx.x%)	N (xx.x%)	N (xx.x%)	
1	N (xx.x%)	N (xx.x%)	N (xx.x%)	
2	N (xx.x%)	N (xx.x%)	N (xx.x%)	
3	N (xx.x%)	N (xx.x%)	N (xx.x%)	

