**Final Analysis Table 3.1.3**  
**Primary Efficacy**  
**Time to first 1st Respiratory hospitalization**  
**Kaplan-Meier Plot**

**CLEANUP-IPF Study**  
**Final Analysis Table 3.1.4**  
**Primary Efficacy**  
**Time to first 1st Non-elective hospitalization**  
**Kaplan-Meier Plot**

**CLEANUP-IPF Study  
Final Analysis Table 3.2  
Primary Efficacy  
Model Analysis**

Comparison	Estimate with 95% Confidence Interval	Test Statistic	Nominal P-Value
Time to 1st Respiratory hospitalization or Death			
Hazard ratio of Oral antimicrobial therapy vs. Standard Care	xx.xx (xx.xx, xx.xx)	xx.xx	x.xxx
Time to first 1st Respiratory hospitalization			
Hazard ratio of Oral antimicrobial therapy vs. Standard Care	xx.xx (xx.xx, xx.xx)	xx.xx	x.xxx
Time to first 1st Non-elective hospitalization			
Hazard ratio of Oral antimicrobial therapy vs. Standard Care	xx.xx (xx.xx, xx.xx)	xx.xx	x.xxx
Total Respiratory hospitalizations			
Rate of Oral antimicrobial therapy	xx.xx (xx.xx, xx.xx)	xxx.xx	
Rate of Standard Care	xx.xx (xx.xx, xx.xx)	xxx.xx	
Ratio of Oral antimicrobial therapy vs. Standard Care	xx.xx (xx.xx, xx.xx)	xx.xx	x.xxx
Total Non-elective hospitalizations			
Rate of Oral antimicrobial therapy	xx.xx (xx.xx, xx.xx)	xxx.xx	x.xxx
Rate of Standard Care	xx.xx (xx.xx, xx.xx)	xxx.xx	x.xxx
Ratio of Oral antimicrobial therapy vs. Standard Care	xx.xx (xx.xx, xx.xx)	xx.xx	x.xxx
Total Respiratory infections			
Rate of Oral antimicrobial therapy	xx.xx (xx.xx, xx.xx)	xxx.xx	x.xxx
Rate of Standard Care	xx.xx (xx.xx, xx.xx)	xxx.xx	x.xxx
Ratio of Oral antimicrobial therapy vs. Standard Care	xx.xx (xx.xx, xx.xx)	xx.xx	x.xxx

**CLEANUP-IPF Study  
Final Analysis Table 4.1.1  
Secondary Efficacy  
FVC and DLCO  
Descriptive Summary**

Parameter Visit Statistic	Oral antimicrobial therapy N= NEVAL	Standard Care N= NEVAL	All Patients N=NEVAL	P-Value
FVC (liters)				
Baseline				
N	xx	xx	xx	x.xxx
Mean (SD)	x.xx (xx.x)	x.xx (xx.x)	x.xx (xx.x)	
Median (Q1, Q3)	x.xx (x.xx, x.xx)	x.xx (x.xx, x.xx)	x.xx (x.xx, x.xx)	
Week 12				
N	xx	xx	xx	x.xxx
Mean (SD)	x.xx (xx.x)	x.xx (xx.x)	x.xx (xx.x)	
Median (Q1, Q3)	x.xx (x.xx, x.xx)	x.xx (x.xx, x.xx)	x.xx (x.xx, x.xx)	
Week 24				
N	xx	xx	xx	x.xxx
Mean (SD)	x.xx (xx.x)	x.xx (xx.x)	x.xx (xx.x)	
Median (Q1, Q3)	x.xx (x.xx, x.xx)	x.xx (x.xx, x.xx)	x.xx (x.xx, x.xx)	
FVC % Predicted				
Baseline				
N	xx	xx	xx	x.xxx
Mean (SD)	x.xx (xx.x)	x.xx (xx.x)	x.xx (xx.x)	

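### SAP secondary endpoints #4, #5 and #8: the Poisson models for total counts do not put time at risk into the model, and the planned fit check has no consequence if the counts are overdispersed

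*SAP*

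**What the plan says.** SAP section VIII specifies Poisson regression for each count endpoint. For #4: "The outcome is the total number of non-elective respiratory hospitalizations with model terms for treatment arm, baseline measurement, and covariates". For #5: "The outcome is the total number of non-elective all-cause hospitalizations with model terms for treatment arm, baseline measurement, and covariates". For #8: "The outcome is the total number of respiratory infections with model terms for treatment arm, baseline measurement, and covariates". Results are to be given as follows: "Rates and 95% confidence intervals will summarize the differences between treatment arms". Mock Table 3.2 has rows such as "Rate of Oral antimicrobial therapy" with no time unit and no person-time column.

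On the end of follow-up, #4 and #5 say that mortality and last-visit information will exist and add lung transplantation as a censoring variable. #8 has neither statement, but protocol 11.2 censors every endpoint at transplantation. None of the three says how these dates enter a count model.

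On model fit, all three say: "The validity of this model in terms of meeting modeling assumptions will be assessed via standard modeling diagnostics and goodness-of-fit measures". No threshold or fallback is given. The one action in that paragraph, a transformation, belongs to the linearity check of continuous covariates.

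Protocol 11.4 covers time-to-event and continuous outcomes and leaves the rest to the SAP. The 2020 addendum does not touch these models.

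**The concern.** Two separate things can go wrong.

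**Time at risk.** Follow-up is meant to vary by patient, from 12 months upward, and is cut short by death, transplant and the early close-out. A Poisson model for a total count without an offset compares events per patient, not events per unit of time. If one arm is followed for less time, it shows fewer events for that reason alone.

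**Variance.** Plain Poisson regression takes the variance to equal the mean. If some patients are admitted repeatedly and others never, the variance is larger and the intervals are too narrow. An offset does not correct this. A check without a stated consequence leaves the choice of model until the data are seen.

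The stakes are limited. These are secondary endpoints with nominal p-values in Table 3.2. The Cox models for #2 and #3 give a first-event cross-check for #4 and #5, though nothing does so for #8.

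**Working it through.** The plan states no rate, dispersion or power for the count endpoints, so there is no figure of its own to reproduce here. As a check on the shared design inputs, protocol Table 1 reproduces within 2 points of power for all nine rows (exponential rates, 30-month even accrual, 12-month minimum, 2% drop-out per year).

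**Inputs from the documents.** 250 patients per arm; two-sided 5%; follow-up uniform over 12–42 months, capped at the 36 months of protocol section 8; drop-out 0.02 per year; and, from protocol 11.3, "placebo group events rates varying from 24% to 36" per cent at 12 months for the composite.

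**Assumptions.** Death hazard 0.10 per year, and between-patient (gamma) frailty variance v of 0, 0.25, 0.5 or 1. The documents give neither.

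**Step 1: event rate L per patient-year for #4.** Solve 1 − exp(−0.10)·(1 + vL)^(−1/v) = p. For v = 0.5 and p = 0.30: 0.70/0.9048 = 0.7736, so L = (0.7736^(−0.5) − 1)/0.5 = 0.27. For p = 0.24 and 0.36, L = 0.18 and 0.38.

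**Step 2: variance inflation with an offset.** φ = 1 + vL·E[t²]/E[t]. Integrating the follow-up distribution with hazard 0.10 + 0.02 gives E[t] = 1.914 years and E[t²] = 4.312, ratio 2.253. For v = 0.5 and p = 0.30: φ = 1 + 0.5 × 0.274 × 2.253 = 1.31.

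**Step 3: actual type I error.** α = 2(1 − Φ(1.96/√φ)). For φ = 1.31: 1.96/1.144 = 1.713, so α = 8.7%.

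Unadjusted, plain Poisson with offset (simulation of 10,000 null trials per cell; p = 24 / 30 / 36%):

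| v | closed form | simulated |
|---|---|---|
| 0 | 5.0 / 5.0 / 5.0% | 4.9 / 4.8 / 5.1% |
| 0.25 | 6.2 / 6.8 / 7.4% | 6.3 / 6.7 / 6.8% |
| 0.5 | 7.4 / 8.7 / 10.1% | 7.2 / 8.8 / 9.9% |
| 1 | 10.1 / 12.8 / 15.9% | 10.2 / 13.0 / 15.8% |

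At v = 0.25–1, offset plus sandwich variance gives 5.1–5.5%, and negative binomial with offset 5.0–5.6%.

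**Step 4: sensitivity.** With death of 5% or 15% per year the simulated error is 6.2–10.5% at v = 0.5 and 8.3–17.8% at v = 1. With follow-up shortened to 3–33 months to mimic the close-out it is 6.4–8.7% and 8.3–12.9%. For #5, at an assumed 1.5 times the #4 rate, it is 8.3–12.6% and 11.8–20.3%. #8 has no anchor in the documents.

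**Step 5: covariate adjustment.** The SAP model is adjusted. If one standard-normal covariate with assumed log rate ratio 0.5 absorbs part of the same total heterogeneity, the residual variance is (1 + v)/exp(0.25) − 1, which is 0.17 for v = 0.5 and 0.56 for v = 1. Simulated error is then about 6–7% and 9–14%.

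**Step 6: no offset.** With equal mortality the null ratio is 1.00, and type I error rises by a further 0.6–1.8 points. With unequal mortality and death independent of frailty, the null ratio is the ratio of mean times at risk: 1.871, 1.810 and 1.715 years at hazards 0.12, 0.15 and 0.20, against 1.914 at 0.10. Second case: frailty at v = 1 also drives death.

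| Death per year, treated vs control | independent: no offset / offset | frailty-driven: no offset / offset |
|---|---|---|
| 12% vs 10% | 0.98 / 1.00 | 0.96 / 0.98 |
| 15% vs 10% | 0.95 / 1.00 | 0.91 / 0.96 |
| 20% vs 10% | 0.90 / 1.00 | 0.84 / 0.92 |

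**The case against.** The best defence is that the intention is clear enough. The results are called rates, and #4 and #5 name mortality, last visit and transplantation, which are the dates that end time at risk; protocol 11.2 brings transplantation to #8. It would therefore be too strong to infer that time at risk is left wholly undefined. The gap is narrower: no text puts those dates into the model. This part of the defence succeeds, but it does not help with variance.

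Second, nothing shows that events cluster. Mock Table 3.1 has the heading "Patients with one of more Number per patient" and rows for 0 to 3 events, but it is a template, and repeat events also occur under a pure Poisson process. At v = 0 the planned model holds its 5%. This stands: overdispersion is a risk to provide for, not a finding.

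Third, adjustment for baseline lung function should absorb some heterogeneity. This also stands and lowers the inflation, as step 5 shows, without removing it.

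Fourth, the SAP promises supportive analyses for informative censoring in all three endpoints. That bears on the last column of step 6, though the analyses are unspecified, and it does not address variance.

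A reader might infer from the termination letter that the ratios favour the intervention falsely. The letter reports an unquantified trend to higher mortality in that arm and no clear harm signal, so the size of any difference in follow-up is unknown. A reader might also tie in the 36- and 42-month maxima. That is a separate discrepancy: an offset built from actual dates needs neither, and a 42-month maximum moves the simulated error only to 7.4–10.3% and 10.2–16.3%.

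**Conclusion.** The concern holds in a limited form. For #4, #5 and #8 the SAP names a plain Poisson model, does not state an offset, and attaches no action to a failed fit check.

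If events cluster, the unadjusted type I error for #4 is about 6–10% at frailty variance 0.5 and 10–16% at 1 even with an offset, or about 6–7% and 9–14% if a prognostic covariate takes up part of the same heterogeneity. Without clustering it is about 5%. Robust variance holds about 5–6%. These figures rest on assumed frailty and 10% yearly death; only the composite event rate comes from the documents.

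Bias from omitting the offset needs unequal follow-up between arms. With equal mortality there is none.

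The documents do not support saying that Poisson regression is wrong in itself, that these intervals are in fact too narrow in this trial, or that the reported ratios are biased. The primary endpoint is not affected.

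**What to change.** For all three endpoints, fit Poisson regression with sandwich variance, or negative binomial regression, and name one. Use as offset the log of time from randomization to the earliest of death, transplantation or last visit. Count only events inside that window, and report mean follow-up per arm beside each ratio.

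The addendum is dated 29 May 2020, after termination and with database lock planned by May 2020. The change should therefore be recorded with a date before these endpoints are analysed, or reported as a sensitivity analysis.

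The cost is a sentence per endpoint and standard software options; the dates are already needed for censoring. When counts are overdispersed, intervals widen by about 9–19% at frailty variance 0.5 and 19–38% at 1 unadjusted, or about 4–8% and 13–27% adjusted with total heterogeneity held fixed. Without overdispersion the cost is near zero. The offset does not remove all bias when sicker patients both die and are admitted more often (last column of step 6), so the promised supportive analyses should be specified with that case in mind.
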